5.0 STEP-KOA Intervention

5.1 Overview_ We have chosen intervention Steps that are evidence-based and focus on enhancing physical activity but differ in the amount, type and mode of care provided. We have chosen three-month intervals for the Steps, based on prior research indicating this is an adequate time period to observe meaningful changes in pain and function⁶¹. All participants in STEP-KOA will continue to have access to the Step 1 program for the full nine-month intervention period, regardless of whether they progress to Steps 2 and 3. This is because VET-KOA may serve as a complementary resource to participants who go on to receive telephone counseling and in-person PT visits; this approach is similar to other stepped care interventions^{33,35}. Further, continued access to VET-KOA is of minimal cost and would be feasible for the VA to provide to Veterans on a longer term basis. Some participants who initially meet response criteria at the three-month assessment point (and therefore remain at Step 1) may regress by six months and no longer meet benchmarks when compared to baseline pain and function. Since these patients initially met response criteria after Step 1, one likely reason for regression is encountering barriers to maintaining activity. These patients will be advanced to the Step 2 intervention at the six-month time point, since the telephone counseling intervention is aimed at addressing multiple types of barriers (Figure 2); this approach is also similar to other stepped care interventions^{33,35}.

We have chosen the OMERACT-OARSI responder criteria to determine which patients progress to Step 2 and Step 3 interventions³⁶. These criteria were established using a combined data-driven and expert opinion approach, and they have been used in over 30 clinical trials of behavioral, pharmacological and surgical interventions for OA (e.g.^{2,62}). The validity and utility of these criteria have been supported in these trials, based on expected proportions of responders to various interventions, as well as the presence of expected associations between patient characteristics and response / non-response. We purposefully selected the OMERACT / OARSI criteria for stepping, rather than physical activity based criteria, for three reasons. First, OMERACT / OARSI criteria cover domains of pain and function, which are treatment goals and outcomes of high importance to patients with OA, as well as their providers. The ultimate goal of the STEP-KOA intervention is to improve these outcomes, with physical activity enhancement being the mechanism. Second, prior studies indicate that physical activity interventions can produce meaningful change in pain and functional outcomes in the context of OA, regardless of other concurrent treatments²⁰. Third, it is possible that some patients could increase physical activity but not achieve meaningful improvement in pain and functional outcomes. A likely reason for such a discrepancy is the need for more targeted physical activity to address specific deficits; this could be addressed by Step 1 and Step 2 interventions. Patients can meet OMERACT-OARSI response criteria in two ways: **1)** $\geq 50\%$ improvement in pain OR function AND absolute change ≥ 20 , **2)** Improvement in at least two of the following: pain $\geq 20\%$ and absolute change ≥ 10 ; function pain $\geq 20\%$ and absolute change ≥ 10 ; patient's global assessment $\geq 20\%$ and absolute change ≥ 10 . Based on prior research^{2,63,64}, we estimate that about 1/3 of participants will meet OMERACT-OARSI response criteria after Step 1 and an additional 1/3 (2/3 of total) will meet response criteria after Step 2. However, *the success of this study is*

not dependent on the responder rate; rather, this rate will provide important information for resource allocation if the STEP-KOA is implemented. We note that the OMERACT-OARSI response criteria include two components of our primary outcome (WOMAC). However, we have purposefully chosen alternate pain and function scales to evaluate OMERACT-OARSI response criteria, so that the primary study outcome is distinct from the scales used to determine progression to more intensive Steps. The project coordinator, not blinded to study assignment, will inform patients via telephone about whether they progress to Step 2 and 3.

5.2 Step 1: VET-KOA. Step 1 involves access to the VET-KOA program described above, with some modifications including no use of email messages. We chose an internet-based program for Step 1 for several reasons. First, there has been increasing and successful use of the internet to deliver physical activity and other behavioral programs,⁶⁵ including recent studies among older adults⁶⁶⁻⁶⁸; this approach also aligns with the VA's current movement toward mobile health behavioral interventions⁶⁹. Second, internet-based programs can be delivered widely at low cost. Third, internet-based programs enhance access by removing transportation related barriers and offering flexibility in terms of the times in which patients can access the program. Fourth, internet-based programs have the capability of tailoring activities to individuals' preferences and abilities; this is important because research has supported the utility of a tailored approach to physical activity⁷⁰. After minor changes, recommended by our Veteran "testers", are made to the VET-KOA program, we will ask an additional 10 Veterans with knee OA to use the website from home for about two weeks and provide feedback on usability. Any additional recommended changes will be incorporated prior to beginning the trial. Prior to the beginning of recruitment, the Durham VAMC Information Security Officer will review the website to determine if it meets all VA information security requirements.

Participants will be given an individualized code and instructions for accessing VET-KOA. They will also be given ankle weights and therapy bands (as in the pilot study), since these are utilized in some exercises. Participants will be given a telephone number to contact the project coordinator if they need technical support regarding the website. These telephone contacts will not involve advisement regarding physical activity and will not be handled by the exercise counselor. We will document the frequency and nature of these contacts, which will be useful in the overall evaluation of this internet-based resource. Participants will be encouraged to access the system as soon as they are randomized and throughout the study period. In accordance with guidelines for physical activity⁵⁸, we will recommend that participants complete stretching and strengthening exercises, guided by the VET-KOA website, at least three times per week. Participants will be told that it is safe and appropriate to perform aerobic exercises daily, or as often as possible, guided by the VET-KOA website. *An overall guiding principle is that participants will be encouraged to be as physically active as their abilities, health conditions, and pain allow, with an emphasis on reducing inactivity and sedentary behavior.*

When participants enter the VET-KOA website, they will be given information on principles of safe, effective physical activity, benefits for patients with knee OA (addressing *Outcome Expectations*), management of pain that may occur with physical activity (addressing *Barriers Self-Efficacy*), and dealing with general barriers to activity (addressing *Barriers Self-Efficacy*). Tailoring of the exercise program in VET-KOA is important for addressing *Exercise Self-Efficacy*; recommending exercises at appropriate levels will help to give participants confidence, especially early in the program, that they can complete these activities. If participants do not enter the website for two weeks, they will receive a telephone call from a study team member encouraging them to access the website, and most importantly to remain physically active. We may also contact the participants if we need to give them information about safety (e.g., if they are recording pain frequently in the website). Selected study team members will have access to a password-protected website that will include information on participants' use of the VET-KOA website, along with any safety-related information. There will be no PHI on this website; participants will be indicated by a unique ID only. If a study participant cannot be reached by telephone, we will leave a voicemail message asking for the participant to call the study team member. We will not leave any PHI on the voicemail message or with a family member.

5.3 Step 2 Intervention: Telephone-Based Physical Activity Counseling. Participants who progress to Step 2 will receive bi-weekly telephone calls from an exercise counselor for a three-month period. We have chosen this Step 2 intervention approach because studies indicate that personal support from an exercise counselor (or similar role) can improve physical activity⁷¹. Also, although this approach is more resource intensive than

an internet-based program, it is less costly than in-person PT visits and does not require Veterans to travel to a VA facility. The overall goals of Step 2 calls are to address any OA or health-related difficulties participants are having with an exercise program, provide additional *Social Support for Physical Activity*, augment *Barriers Self-Efficacy* by providing additional personalized counseling for the specific barriers, and reinforce information about the benefits of physical activity (*Outcome Expectations*). During the first phone call the exercise counselor will query participants about whether OA symptoms or other health problems have presented challenges to their engagement in exercise. The counselor will have access to participants' baseline study assessments, which include information on comorbid health conditions and other joints with arthritis; this will help the counselor to probe for potential barriers. It is also common for individuals with OA to face challenges to exercise due to their pain and functional limitations. Therefore, the counselor will work with participants to tailor the exercise types and intensity to accommodate any of these difficulties. The exercise counselor will also ask participants about any other general barriers they encountered in completing their physical activity since the last call (e.g., time demands). The exercise counselor will guide participants in a process of problem-solving any barriers, and this will be incorporated into the process of developing action plans for the following weeks. Motivational interviewing strategies, including use of open-ended questions and reflective listening, will be employed to identify any ambivalence patients experience about engaging in physical activity⁷². We have used these strategies in our studies that include telephone-based physical activity counseling²⁶. During each telephone call, the exercise counselor will also engage participants in a process of goal-setting and action planning for their weekly physical activity, using "SMART" principles that emphasize that goals need to be Specific, Measurable, Action-oriented, and Time-Bound³⁹. The exercise counselor will help participants to develop goals and action plans that are reasonable for them to achieve, facilitating *Exercise Self-Efficacy*.

We expect most calls will take about 15-20 minutes and will document the duration of each call so that we can calculate the overall effort required to complete this intervention Step. The first call will likely be longer since the counselor will take time for introductions and to explore current exercise and challenges. The exercise counselor will encourage the participants to invite a friend or family member to be involved with calls if they would like.

5.4 Step 3 Intervention: PT Visits. We have chosen this Step 3 intervention approach because physical therapists have specialized training to evaluate functional impairments and biomechanical issues and can assist patients with tailoring exercises to address these deficits. Physical therapists can also evaluate patients' needs for knee braces, shoe lifts, or other assistive devices. We posit that patients who do not experience meaningful improvement after remotely delivered physical activity interventions may have greater functional impairments or other underlying clinical issues that will benefit from in-person attention by a physical therapist.

We have based this intervention on usual PT care for knee OA within the VA healthcare system, as well as processes we have utilized in a clinical trial at the Durham VAMC⁴⁴. Core components of PT for knee OA include: instruction in a tailored exercise program, instruction in activity pacing and joint protection, and evaluation of: mobility, stability, function, knee alignment, limb length inequalities, specific areas of weakness or inflexibility, and need for mobility aids, knee braces, and shoe orthotics. Participants will receive approximately 3-7 PT visits; the first will be about hour and the remaining visits will be about 30 minutes. Participants will be paid \$10 for each physical therapy visit, plus an additional amount that varies by distance traveled (as specified in the consent form). The number of visits will be based on participants' progression and need for additional follow-up. Components of the physical therapy sessions will include:

1. Standard assessments including range of motion, strength, knee alignment, limb length equality, balance, and gait.
2. Review the participant's current exercise and provide recommendations for tailoring
3. Examine participants' affected knee(s) for edema and provide appropriate recommendations for the use of heat, cold, elevation, and / or self-massage, particularly to be used before or after exercises.
4. Observation of participants as they perform strengthening and stretching exercises to ensure proper technique.
5. Provision of recommendations for referrals to:
 - a. Prosthetics for assistive device (if participants experience balance or instability with walking)
 - b. Prosthetics for knee brace (if participants experience knee instability or significant malalignment)

- c. Podiatry for shoe orthotics / lifts (if participants have a limb length inequality)
- 6. Instruction in activity pacing and joint protection.

PT visits can impact multiple factors associated with physical activity as outlined in the Social Cognitive Model. Specifically, these visits provide more intensive and personalized instruction in a home exercise program, which can bolster both *Exercise Self-Efficacy* and *Barriers Self-Efficacy*. Physical therapists also provide additional *Social Support for Physical Activity* and help participants to have an understanding of long-term benefits of physical activity for knee OA (*Outcome Expectations*). Finally, these visits provide additional instruction on managing pain that can occur with physical activity, addressing *Somatic Sensations*.

As of February 14, 2018, we are no longer able to provide study-specific PT at the Greenville VA Healthcare Center due to lack of an available study physical therapist. Participants may come to the Durham VA for study-provided PT, and we will compensate them additionally to account for the travel (based on mileage rates already specified in our consent form). If a participant opts not to come to the Durham VA for study PT, a clinical member of the study team may contact the participant's PCP to notify them about the participants' inability to receive physical therapy as part of study-related procedures. The PCP will also be notified that it is up to their discretion regarding whether to refer the patient to PT, as clinically appropriate. (Study-provided PT was designed to mirror routine PT for knee osteoarthritis, so the type of care that patients would receive should not differ substantially if it is provided through a typical clinical route at the VA.) If participants do not want to participate in either option, they can still remain in the study if they choose, and we will inform them that this will not have any impact on their usual care at the VA. Because some patients will not move on to Step 3 of the intervention (PT), we will inform participants of these options at the 6-month follow-up point, via phone (using a script), if the information is relevant for them.

6.0 Arthritis Education Intervention

Participants in the AE control group will receive low literacy educational materials via mail every two weeks. Because STEP-KOA is a multi-component intervention, with participants receiving different numbers of Steps, it is not possible to implement a control condition that will mirror the exact intervention "dose" received by all participants in the STEP-KOA group. However, AE will achieve the goal of providing an active, OA-related control condition. We selected a mail format because it mirrors the "remote" aspect of the Step 1 intervention that will be received by all study participants in the STEP-KOA group. We selected the two week interval for mailings because it mirrors aspects of each of the STEP-KOA interventions: Step 1 includes feedback regarding potential changes in exercise level on a two-week basis, Step 2 involves biweekly phone calls, and Step 3 involves PT visits spaced approximately 2 weeks apart. The AE intervention will include a comprehensive set of topics related to OA and its management, based on established treatment guidelines (Box 1)^{17,73}. These materials will be based on those we have already developed and successfully utilized in prior HSR&D funded clinical trials among Veterans with OA^{16,26}.

Box 1. Topics for AE Intervention

- What is OA?
- Diagnosis of OA
- Risk Factors for OA
- Health Care Providers And OA
- Pain Medications (Oral)
- Topical Pain Medications
- Joint Injections
- Knee Braces
- Shoes and Orthotics
- Physical Activity
- Weight Management
- Joint Protection
- Pain Coping Skills
- Surgery
- Complementary and Alternative Therapies
- OA and Sleep
- OA and Mental Health
- OA and Fatigue

7.0 Measures

Study assessments will be conducted in person at baseline and 9-months (primary outcome point); interim assessments (3-months, 6-months) and longer-term follow-up (15-months) will be conducted via telephone. Assessments will be conducted by a research assistant blinded to group assignment. Participants will be paid \$40 for in-person and \$20 for telephone-based assessments. This measurement battery is shorter in length than those from our recent clinical trials among veterans with knee OA^{26,44}, and the time burden has been

acceptable to participants, with little missing data. Prior to each assessment point (either on the phone at the time of scheduling, on the phone just before assessments begin, or in-person at the time of assessment), a study team member will ask participants whether they have had any new health problems since their last assessment point. If there are new health problems, the study team will ask the nature of these problems. If these problems are related to exclusion criteria, the study team member will either: 1) Let the participant know they need to be withdrawn from the study OR 2) If it is unclear whether withdrawal is appropriate, let the participant know they will contact a clinical co-investigator and follow-up to let them know if they are eligible to continue in the study; assessments will not proceed until this is resolved. At in-person follow-up visits, research assistants will measure the participants Resting Blood Pressure; if diastolic blood pressure >110mm/Hg or systolic >200mm/Hg will be advised to be seen at the Emergency Department or Urgent Care immediately. Assessments will not proceed until these issues are resolved.

7.1 Primary Outcome: WOMAC. The primary outcome measure is the WOMAC, a measure of lower extremity pain (5 items), stiffness (2 items), and function (17 items), with items rated on a Likert scale of 0 (no symptoms) to 4 (extreme symptoms). The reliability and validity of the WOMAC total score and subscales have been confirmed⁷⁴. The WOMAC has been widely used in trials behavioral interventions for knee OA, confirming its sensitivity to change. The WOMAC has also been validated for use via telephone⁷⁵. To supplement the WOMAC, we will add additional measures that are part of the widely used Knee Osteoarthritis Outcome Survey (KOOS).

7.2 Secondary Outcome: Objective Physical Function. We will assess physical function using measures recommended by OARSI for clinical trials of knee OA⁷⁶. These tests have been previously validated, with strong measurement properties and sensitivity to change in clinical trials among patients with OA. These tests will include a 30 second stair stand test, a 40m fast-paced walk, a timed get up and go test, stair climbing test, and a 6-minute walk test, following previously established procedures for each. The 30 second stair stand asks participants to rise and sit back down in a chair as many times as they can during that time period, without using hands or arms for support⁷⁷. The 40m fast-paced walk is a timed test of walking twice back and forth (as fast as participants are able) over a 10m distance⁷⁸. The timed get up-and-go test requires the participants to stand from a standard arm chair, walk 3 meters and then return to sitting in the same chair (as quickly and safely as possible). The stair climbing test measures the time it takes to ascend and descend a flight of 12 steps (each step 18 cm high and 28 cm deep). Participants will be asked to complete the test as quickly as they felt safe and comfortable. The use of one handrail will be allowed if necessary, but patients will be encouraged to minimize their use of the handrail. The 6-minute walk test will require participants to walk as far as they can during a 6-minute periods. Walking aids are permitted as needed. Participants will be asked to walk the amount of time they are able to walk. Following these tests, we will ask participants to indicate the maximum pain they experienced, on a scale of 0-10, during the test.

7.3 Self-Efficacy for Exercise Scale. The Self-Efficacy for Exercise scale assesses individuals' confidence in engaging in exercise in nine different situations that could present barriers (including having pain when exercising)⁷⁵. For each situation, individuals are asked to rate their confidence in being able to exercise three times a week for 20 minutes each time, on a scale of 0 (not confident) to 10 (very confident). Validity of this measure was confirmed by expected associations with actual exercise, as well as physical and mental health.

7.4 Social Support for Exercise Scale. This scale includes 13 items that assess the frequency with which friends and family members (separately) engage in behaviors that may either support exercise (e.g., "Gave me encouragement to stick with my exercise program") or discourage exercise (e.g., "Complained about the time I spend exercising"). All items are measured on a scale of 1 (none) to 5 (very often). The scale has shown acceptable test-retest reliability and internal consistency reliability. In addition, the scale was correlated with exercise habits, providing evidence of concurrent criterion-related validity.

7.5 Hopkins Rehabilitation Engagement Rating Scale (HRERS), a 5-item, clinician-rated measure developed to quantify engagement in acute rehabilitation services. This will be completed by the telephone counselor at the end of the Step 2 and by physical therapists at the end of Step 3, for participants involve in those steps only.

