Hypothesis 2: At 15-months, Veterans in the STEP-KOA group will maintain improvements in WOMAC scores achieved at 9 months (i.e. there will be no estimated mean difference in WOMAC scores between 9 and 15 months). We will estimate these differences in WOMAC scores for the full STEP-KOA group as well as for subgroups defined by the combination of steps received during the STEP-KOA program.

Specific Aim 3: To describe patients who are non-responders at each Step in the STEP-KOA group, and to examine patient characteristics associated with non-response.

Specific Aim 4: To examine the cost effectiveness of overall STEP-KOA intervention, compared with the AE control group.

This study will have an important impact for Veterans because it evaluates a novel, patient-centered approach to improving physical activity and related outcomes for knee OA – one of the most common and disabling health problems. The study will have an important impact for the VA because the STEP-KOA could be a practical approach for both improving access to physical activity interventions and targeting more costly and limited PT resources for knee OA in an evidence-based manner.

RESEARCH PLAN

A. BACKGROUND AND CONTEXT

1.0 Osteoarthritis (OA) is Highly Prevalent and Disabling.

Osteoarthritis is one of the most prevalent chronic conditions in the U.S. Knee OA is particularly common, with one study indicating a lifetime risk of 45%,^{1,2} and the prevalence of knee OA is expected to rise dramatically over the next several decades³. OA is associated with significant pain, functional limitations, and reduced health-related quality of life⁴. It is the most frequently reported cause of disability in the U.S.⁵. Among older adults, the risk of disability attributable to knee OA is as great as that due to cardiovascular disease and greater than any other medical condition⁶. OA is also associated with significant costs to both patients and health care systems. Annual health care expenditures of individuals with OA are about twice as high as individuals without OA, even when adjusting for age and gender⁷.

2.0 Osteoarthritis is a Particular Burden in Veterans.

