assessments will be used to determine whether participants in STEP-KOA need to progress to more intensive steps. The primary outcome point (Aim 1) will be at nine months. In addition, Aim 2 will examine whether any effects are maintained in the STEP-KOA group in the six months following the intervention period (15 months post-randomization). A six-month follow-up period is meaningful for assessing maintenance in the context of physical activity trials among patients with OA^{56,57}, and it is feasible to complete within the study period. Following completion of 9-month assessments, participants assigned to the AE control group will receive access to the internet-based exercise training program, along with the Step 2 exercise counseling calls. (Therefore, the AE group will not complete 15-month assessments, as Aim 2 will now include the STEP-KOA group only.) We chose to provide treatment to the AE group after nine months because 15 months was deemed to be an overly long waiting period in the context of a symptomatic condition; this not only raises ethical concerns but scientific ones, since a long wait list period would increase the likelihood of participants seeking physical therapy outside the context of the study during that time frame. We acknowledge that this strategy means that we will not be able to test between-group differences at a longer-term, 15-month follow-up period. However, we will still gain valuable information by assessing whether any changes observed within the STEP-KOA group are maintained over time (9-months to 15-months) and whether this may differ among participants exposed to the different Steps of the program. All participants will continue other usual medical care for OA during the full study period, as recommended by their providers.

2.0 Study Sites. This study will be conducted in two sites in the VA Mid-Atlantic Health Care Network (VISN 6), Durham, NC and Greenville, NC, to enhance generalizability. The Durham VAMC is more urban, and the Greenville VAMC (also known as the Greenville Health Care Center) is located in a more rural and coastal region. Participants will be able to select a different study site from the one originally assigned if their location is closer to the other site.

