Effectiveness Measures. We will use two effectiveness measures to calculate cost effectiveness ratios: WOMAC units (described above) and the EuroQoL EQ-5D-5L questionnaire. The EuroQoL health outcome measure (EQ-5D-5L and EQ-VAS) allows us to calculate quality-adjusted life years (QALYs), and it has been used successfully in previous research among patients with arthritis ⁸².

7.12 Participant Feedback on STEP-KOA. We will ask open-ended questions regarding the intervention components. For example, we will ask participants about usability of the VET-KOA website, appropriateness of the number and length of telephone sessions with the exercise counselor, content of PT visits, and ways we can improve the interventions.

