8.0 Data Analyses

8.1. General Considerations. Primary study analyses will be conducted on an intent-to-treat basis, with participants analyzed in the group to which they were assigned. Additional exploratory analyses focusing on more restrictive analytic cohorts (e.g., per protocol analysis) will be considered, to provide additional information about the impact of magnitude of exposure to the intervention. The main conclusions drawn from this trial will be based on the pre-specified primary and secondary hypotheses outlined below and will be tested with two-sided p-values at the standard 0.05 level unless noted otherwise. Statistical analyses will be performed using SAS for Windows (Version 9.2: SAS Institute, Cary, NC) and R (<http://www.R-project.org/>).

8.2. Primary Analysis (Specific Aim 1). The main study outcome, WOMAC, is a continuous measure collected at baseline, 3, 6, 9 and 15 months (STEP-KOA group only). For the primary hypothesis we will examine STEP-KOA effects at the 9-month assessment. We will use a linear mixed model (LMM) that accounts for the correlation between a participant's repeated outcome measurements over time. We will apply an unstructured covariance matrix to take into account the within-patient correlation between repeated measures. The fixed-effect portion of the model will have the form: $Y_{it} = \beta_0 + \beta_1 3\text{month} + \beta_2 6\text{month} + \beta_3 9\text{month} + \beta_4 \text{STEP-KOA} * 3\text{month} + \beta_5 \text{STEP-KOA} * 6\text{month} + \beta_6 \text{STEP-KOA} * 9\text{month}$, where Y_{it} is the WOMAC score for subject i at $t=0, 3, 6, \text{ and } 9\text{months}$. We will estimate the parameters in the model and set up contrasts for tests of hypotheses using the SAS procedure MIXED (Cary, NC). Specifically, for Hypothesis 1, we will test for a difference in mean WOMAC scores between the STEP-KOA and AE groups at 9-months by testing that $\beta_6=0$.

Time is coded in the model to fit a constrained longitudinal data model (cLDA), in which baseline WOMAC score is modeled as a dependent variable in conjunction with the constraint of a common baseline mean across treatment arms⁸³. For improvement in precision, the model will be adjusted for stratification variables⁸⁴.

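### The blinded-assessor statement cannot hold at 15 months, when only STEP-KOA participants are assessed, so the Aim 2 contrast is not assessor-blinded at both of its time points

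*Combined protocol and SAP*

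**What the plan says.** Section 7.0 (Measures) places the baseline and 9-month assessments in person and states that "interim assessments (3-months, 6-months) and longer-term follow-up (15-months) will be conducted via telephone". The next sentence says that "Assessments will be conducted by a research assistant blinded to group assignment". No time point is excepted.

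The Study Design section (C.1.0) explains that after the 9-month assessment "participants assigned to the AE control group will receive access to the internet-based exercise training program", together with the Step 2 counselling calls. It concludes that "the AE group will not complete 15-month assessments, as Aim 2 will now include the STEP-KOA group only". Section 8.2 confirms that the 15-month WOMAC is collected in STEP-KOA only.

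Hypothesis 2 (Specific Aims) is that "there will be no estimated mean difference in WOMAC scores between 9 and 15 months". Section 8.3 plans Aim 2 as a within-arm difference between 9 and 15 months with a 95% confidence interval, overall and by the combination of Steps received.

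Section 7.12 plans open-ended feedback on the intervention; for example, "we will ask participants about usability of the VET-KOA website, appropriateness of the number and length of telephone sessions". It does not say when this is asked, by whom, or in what order relative to the WOMAC.

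**The concern.** Blinding to group is possible only while both groups are being assessed. Once AE has no 15-month assessment, being on the 15-month call list identifies a participant as STEP-KOA. The Study Design section acknowledges that the between-group test at 15 months is lost, but it does not mention that assessor blinding is lost as well. The limitations in Section 12.0 do not mention it either.

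Aim 2 has no control arm at month 15, so a change in measurement conditions between 9 and 15 months would not cancel out of the contrast. The hypothesis is also one of no change, so a small favourable shift at 15 months could look like maintenance. Left as it stands, the plan would allow Aim 2 to be reported as assessor-blinded throughout when it was not.

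The comparison of maintenance by Steps received raises a related matter. Arm cannot be hidden at 15 months, but the Steps a participant received still can be, and the plan does not say that they will be.

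**Working it through.** **Sample size, reproduced for its inputs.** Section 8.5 gives SD 17.5, correlation 0.4 between baseline and follow-up, a 5.8-point difference, two-sided alpha 0.05, 80% power, 2:1 allocation and 20% attrition.

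- Control arm before adjustment: 1.5 × (17.5 × (1.960 + 0.842) / 5.8)² = 107.2.
- Times 1 − 0.4² = 0.84: 90.03, rounded up to 91.
- Attrition: 91 / 0.8 = 113.75, rounded up to 114.
- Total: 3 × 114 = 342, against the stated 345.

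The stated figure is sound and is not in question. The SD, arm sizes and attrition are reused below.

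**Who is assessed at each time point.** With 230 and 115 randomised and 20% attrition in each arm:

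- 9 months: 230 × 0.8 = 184 STEP-KOA and 115 × 0.8 = 92 AE, so 184 / 276 = 67% are STEP-KOA. Being due for assessment does not identify the arm.
- 15 months: 184 STEP-KOA and no AE, so 100% are STEP-KOA. Being due for assessment identifies the arm to anyone who knows the design.

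The documents describe nothing that would restore blinding at 15 months, such as calls to AE participants, self-completion, or an assessor kept unaware of the design.

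**Scale of the Aim 2 contrast.** Treating the 9-to-15-month change as a paired difference with equal SD at both points:

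SE = SD × √(2(1 − r)) / √n, and 95% half-width = 1.96 × SE, with SD = 17.5 and n = 184.

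The correlation r between 9 and 15 months is not in the documents. The only WOMAC correlation given is 0.4, for baseline to follow-up. The range 0.4 to 0.8 is therefore an assumption.

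| r (assumed) | SD of change | SE | 95% half-width |
|---|---|---|---|
| 0.4 | 19.17 | 1.41 | 2.77 |
| 0.6 | 15.65 | 1.15 | 2.26 |
| 0.8 | 11.07 | 0.82 | 1.60 |

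The planned mixed model will not give exactly these values, but they show the order of precision. They say how large a shift would have to be to equal the margin of error. They do not estimate any shift.

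**What else changes between the two points.** Section 7.0 has the 9-month interview in person and the 15-month interview by telephone. Loss of assessor blinding and change of mode coincide exactly, so the data cannot separate one from the other.

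**The case against.** The strongest reply is that assessor blinding matters little here. The WOMAC is rated by the participant, and no participant blinding is described at any time. The person giving the answers knows what they received at 9 and at 15 months alike; only the interviewer's knowledge changes. Arm blinding chiefly protects a between-arm comparison, and Aim 2 has none. Section 7.0 also cites validation of the WOMAC by telephone. All of this stands, and it means that any effect may be modest. It does not make the blinding statement correct at 15 months.

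Three stronger readings are tempting, and the documents do not support them.

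- A reader might infer that an interviewer effect of about 2 points would be enough to create or hide a significant change. No source in the documents gives an effect of that size. Two points is also below the half-width at r = 0.6 (2.26) and at r = 0.4 (2.77). With no true change, a 2-point shift would reach p < 0.05 about 41% and 29% of the time respectively. Section 8.3 in any case frames Aim 2 as an estimate with an interval.
- A reader might infer from Section 7.12 that the 9-month primary outcome is exposed, since the feedback questions reveal arm and Steps. That would require the blinded assessor to ask them before the WOMAC. The plan is silent on timing, order and staff, and silence does not show exposure. Both arms are assessed at 9 months.
- A reader might infer that assessors can see the Steps received. Section 10.0 describes shared systems for tracking and for outcome data but says nothing about assessors' access. Section 5.1 gives the Step-progression calls to an unblinded project coordinator. Access is unstated, not shown.

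**Conclusion.** The point holds for the 15-month assessment only. The blinding statement in Section 7.0 is incompatible with the Study Design section and Section 8.2 at that time point, provided the assessor knows the design; the plan does not say otherwise. Aim 2 therefore compares a 9-month measurement stated to be assessor-blinded with a 15-month measurement open to arm, and the mode of interview changes at the same time.

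Neither the size nor the direction of any resulting bias can be derived. The reference scale is a 95% half-width of about 1.6 to 2.8 WOMAC points. It rests on 184 participants, SD 17.5 at both points and an assumed correlation of 0.8 to 0.4. The sample size and the 9-month primary comparison are not called into question. This is a correctable misstatement affecting a secondary, uncontrolled aim, and correcting it costs almost nothing.

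**What to change.** - In Section 7.0, limit the blinded-assessor statement to baseline through 9 months, and state that the 15-month assessment is open to arm.
- State that the 15-month assessor is kept masked to what can still be hidden: Steps received, responder history and earlier scores. This protects the by-Step maintenance estimates.
- At 15 months, read the WOMAC from a fixed script at the start of the call, and ask any Section 7.12 feedback questions after it. There is no need to prescribe which member of staff asks them.
- Report the loss of assessor blinding and the change from in-person to telephone interviewing as limitations of Aim 2, and note that their effects cannot be separated.

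The cost is protocol wording, a fixed question order and a check on what the assessor can view. No visits or participants are added. The price is a slightly weaker stated design property for Aim 2, which is what the design already delivers.
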